**6.5. Analysis of safety****6.5.1. Analysis of safety planned in the protocol**

The analysis for safety will be performed on the Exposed Set, Solicited and Unsolicited Safety Sets.

The number and percentage of subjects with at least one **local solicited AE**, with at least one **general solicited AE** and with any solicited AE during the 7-day follow-up period after each vaccination, will be tabulated with exact 95% confidence interval (CI), after each vaccination and overall by study group. The percentage of doses followed by at least one local solicited AE, by at least one general solicited AE and by any solicited AE will be tabulated overall by group with exact 95% CIs. The same computations will be done for Grade 3 solicited AEs.

The number and percentage of subjects reporting each individual solicited local and general AE during the 7-day follow-up period will be tabulated with exact 95% CI after each vaccination, overall by vaccine schedule and by severity. The percentage of doses followed by each individual solicited local and general AE will be tabulated overall by group and by severity with exact 95% CIs.

For fever, additional analyses will be performed by 0.5°C increments.

All the unsolicited adverse events occurring within 30 days after each vaccination, judged either as related or not related to vaccination by the investigator, will be recorded.

The verbatim reports of **unsolicited** symptoms will be reviewed by a physician and the signs and symptoms will be coded according to the MedDRA Dictionary for Adverse Reaction Terminology. Every verbatim term will be matched with the appropriate preferred term (PT). The percentage of subjects with at least one unsolicited AE during the 30-day follow-up period after any study vaccination will be tabulated with its exact 95% CI for each group and by MedDRA PT. Similar tabulation will be done for the percentage of subjects, with Grade 3 unsolicited symptoms per dose.

The number of subjects who experienced any **pIMD** or any **SAE** from first vaccination up to 12 months post-Dose 4 will be reported.

**CONFIDENTIAL**207759 (NTHI MCAT-008)  
Statistical Analysis Plan Amendment 1 Final

The number of subjects who experienced any **SAE, death, pIMD** or **AE leading to study withdrawal**, from first vaccination up to study conclusion, and any **SAE related to study participation of concurrent GSK medication/ vaccination**, during the entire study period, will be reported.

In case of **Pregnancy** during the study, data follow-up and pregnancy outcomes will be described in detail.

The percentage of subjects using **concomitant medication/ product associated with an AE** will be summarised per group for each study vaccination and overall study vaccination.

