- Rationale for the study design

Previous studies in the COPD project have evaluated a 2-dose vaccination schedule. The current study will evaluate the safety and immunogenicity of 3 doses of the investigational vaccine. Adults aged 40 to 80 years with a smoking history of at least 10 pack-years, will receive 2 doses of the NTHi-Mcat investigational vaccine at 0 and 2 months in both study arms. Following these 2 doses, one study arm will receive a 3rd dose of the investigational NTHi-Mcat vaccine at 6 months and a placebo control at 12 months (**Schedule 1**) and the other study arm will receive a placebo control at 6 months and a 3rd dose of the investigational NTHi-Mcat vaccine at 12 months (**Schedule 2**).

- Rationale for the use of placebo

The placebo dose is included in the NTHI MCAT-008 study in order to preserve the blind in the evaluation of the two vaccination schedules.

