**5.2.2.2.1. Study group allocation**

The target will be to enrol approximately 200 eligible subjects who will be randomly assigned to two study groups in a (1:1) ratio (approximately 100 subjects in each group).

Allocation of the subject to a study group at the investigator site will be performed using a randomisation system on internet (SBIR).

After obtaining the signed and dated ICF from the subject and having checked the eligibility of the subject, the site staff in charge of the vaccine administration will access SBIR. Upon providing the subject identification number, the randomisation system will determine the study group and will provide the treatment number to be used for the first dose.

The number of each administered treatment must be recorded in the eCRF on the Vaccine Administration screen.

When SBIR is not available, please refer to the SBIR user guide or the Study Procedures Manual (SPM) for specific instructions.

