Note: The double-line border following Day 541 indicates the final analysis which will be performed on all data (i.e. data that are as clean as possible) obtained up to that timepoint.

Vacc: vaccination.

● is used to indicate a study procedure that requires documentation in the individual eCRF.

○ is used to indicate a study procedure that does not require documentation in the individual eCRF.

a This procedure will be performed only if deemed necessary by the Investigator or delegate.

b Only for women of childbearing potential.

c Only for subjects in the sub-cohort for CMI.

d Refer to Section 6.5 for more details on study procedures for subjects meeting contraindications to subsequent vaccination before administration of vaccine Dose 2, 3 and 4.

e Please refer to Section 8.3 for recording periods of local and general solicited AEs, unsolicited AEs, SAEs, (S)AEs leading to study withdrawal, SAEs related to study vaccine(s)/product(s), intercurrent medical conditions, pIMDs and pregnancies.

f Blood sampling must occur prior to vaccination.

g **If a diagnosis of COVID-19 is made in accordance with the current WHO case definition, cases should be reported as AEs or SAEs (refer to Section 8.1 for safety definitions), and routine procedures for recording, evaluation, follow-up, and reporting of AEs, and SAEs should be followed in accordance with the time period set out in Table 16**

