**10.4. Determination of sample size****Primary objective**

In this study, a third injection will be given either at 6 months or at 12 months in order to verify the safety of the third dose.

**CONFIDENTIAL**207759 (NTHI MCAT-008)  
Protocol Amendment 3 Final

Considering the sample size of 100 in each vaccination schedule, [Table 19](#) illustrates the precision we can get on the percentage of subjects with grade 3 symptoms following a third vaccination.

A sample size of 100 subjects allows a 2-sided 95% confidence interval with a width equal to 0.165 when the sample proportion is equal to 20%, using a simple asymptotic formula.

**Table 19** Exact confidence interval for one proportion

| % of subjects with a symptom | N=100 subjects                     |             | N=90 subjects*                     |             |
|------------------------------|------------------------------------|-------------|------------------------------------|-------------|
|                              | Exact 95% Confidence Interval (CI) |             | Exact 95% Confidence Interval (CI) |             |
|                              | Lower Limit                        | Upper limit | Lower Limit                        | Upper limit |
| 0                            | 0.0                                | 3.6         | 0.0                                | 4.0         |
| 5                            | 1.6                                | 11.3        | 1.5                                | 11.7        |
| 10                           | 4.9                                | 17.6        | 4.7                                | 18.1        |
| 15                           | 8.6                                | 23.5        | 8.3                                | 24.1        |
| 20                           | 12.7                               | 29.2        | 12.3                               | 29.8        |
| 25                           | 16.9                               | 34.7        | 16.5                               | 35.2        |
| 30                           | 21.2                               | 40.0        | 20.8                               | 40.6        |
| 35                           | 25.7                               | 45.2        | 25.2                               | 45.8        |
| 40                           | 30.3                               | 50.3        | 29.8                               | 50.9        |

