**Secondary objectives:****Humoral immunogenicity after third dose**

The intent of this secondary objective is to evaluate the improvement of the persistence of antibody response at one month after a third injection. An increase in the antibody titres compared to the second dose is expected.

Approximately a 10% drop out is expected for the third dose evaluation (given at 6 months for one arm and at 12 months for the other arm) and thus 90 evaluable subjects are expected to be analysed for the humoral immunogenicity evaluation.

A sample size of 90 evaluable subjects achieves 90% power to detect a difference of 0.256 between the null hypothesis mean of 0.0 and the alternative hypothesis mean with a known standard deviation of 0.83 and with a significance level (alpha) of 0.05 using a one-sided one-sample t-test.

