**6.4. Immunogenicity****6.4.1. Analysis of immunogenicity planned in the protocol**

The analysis will be performed on the PPS at first line. If the percentage of vaccinated subjects with serological results excluded from the PPS is more than 10%, a second line analysis will be performed on the FAS.

The CMI analysis will be performed on the FAS – CMI Subset.

**CONFIDENTIAL**207759 (NTHI MCAT-008)  
Statistical Analysis Plan Amendment 1 Final**6.4.1.1. Humoral Immunogenicity****6.4.1.1.1. Within groups assessment****ELISA**

For each group, eight timepoints (Day 1, Day 91, Day 181, Day 211, Day 361, Day 391, Day 541 and Day 721, when blood samples are collected) are considered for humoral immune response against the four antigens PD, PE, PilA and UspA2, for which the following will be computed:

- Seropositivity rate and associated 95% CI at each time point (See Additional considerations for seroresponse definition and assay cut-off values).
- GMCs at each time point and their 95% CIs.

With respect to antibody levels at Day 1 (before 1st dose):

- GMRs at each time point and their 95% CIs.
- Percentage of subjects with 2-fold, 4-fold and 8-fold increase at each time point and associated 95% CI.

With respect to antibody levels at Day 181 (before 3rd dose):

- GMRs at Day 211, Day 361, Day 391, Day 541 and Day 721 and their 95% CIs.
- Percentage of subjects with 2-fold, 4-fold and 8-fold increase at Day 211, Day 361, Day 391, Day 541 and Day 721 and associated 95% CI.

With respect to antibody levels at Day 361 (before 4th dose):

- GMRs at Day 391, Day 541 and Day 721 and their 95% CIs.
- Percentage of subjects with 2-fold, 4-fold and 8-fold increase at Day 391, Day 541 and Day 721 and associated 95% CI.

The distribution of antibody concentrations will be displayed using Reverse Cumulative Curves.

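### AE rates after Doses 1 and 2 and antibody summaries up to Day 181 are planned by arm only, although both arms have had the same regimen; a pooled column would narrow the intervals at almost no cost

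*SAP*

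**What the plan says.** The two schedules share their first two injections. The Protocol Synopsis (rationale for the study design) states that subjects "will receive 2 doses of the NTHi-Mcat investigational vaccine at 0 and 2 months in both study arms". Protocol Table 12 shows the first difference at Visit 5 (Day 181), when one arm receives vaccine and the other placebo. Subjects are "randomly assigned to two study groups in a (1:1) ratio" (Protocol 5.2.2.2.1), and Epoch 001 is observer-blind (Protocol 5.3). The Day 181 blood sample still belongs to the common period, because the footnote to Protocol Table 5 requires that "Blood sampling must occur prior to vaccination".

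The SAP reports this period by arm:

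- **Solicited AEs (6.5.1)** "will be tabulated with exact 95% confidence interval (CI), after each vaccination and overall by study group". Here, overall means across doses within a group, not across groups.
- **Unsolicited AEs (6.5.1, 6.5.2.3)** are also given per group.
- **Antibodies (6.4.1.1.1)** are summarised separately for each group and include "GMCs at each time point and their 95% CIs". Section 6.4.2.1 gives seropositivity with Clopper-Pearson limits per group, and model-based GMCs and GMRs per group.
- **Between-group contrasts (6.4.1.1.2)** are planned visit by visit, so they include Days 91 and 181.

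No estimate combining the two arms is described for any of these. Combined summaries do appear elsewhere: medical history (SAP 6.1.2.1), distribution over sites (SAP 6.1.1), and the N = 200 calculation for rare AEs in Protocol Table 20.

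**The concern.** Until the Day 181 injection the trial is in effect a single-arm study of two doses in about 200 randomised subjects. Solicited symptoms after each vaccination are part of the primary endpoint, so the rates after Doses 1 and 2 will be read as results in their own right. Two intervals on about 100 subjects each, and none on 200, describe the two-dose profile less precisely than the data allow. The loss is relatively largest for uncommon Grade 3 symptoms, where the upper limit is what the reader wants.

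A second, smaller matter is presentation. Side-by-side arms, with between-group antibody ratios at Days 91 and 181, invite a reader to interpret differences that arise before the regimens differ.

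**Working it through.** **Inputs.** N = 100 per arm (Protocol 10.4: "Considering the sample size of 100 in each vaccination schedule"), 200 in total; two-sided 95% confidence; exact limits for proportions (SAP 6.5.1, 6.4.2.1); SD 0.83 for the antibody measure (Protocol 10.4, scale not named). Protocol 10.4 also says "Approximately a 10% drop out is expected for the third dose evaluation", so 90 against 180 was checked as well.

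**Reproducing the plan's figure.** Protocol 10.4 says "A sample size of 100 subjects allows a 2-sided 95% confidence interval with a width equal to 0.165" at an observed 20%. The Clopper-Pearson limits are:

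- lower: 2.5% quantile of Beta(x, n − x + 1)
- upper: 97.5% quantile of Beta(x + 1, n − x)

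For x = 20 and n = 100 this gives 12.67% to 29.18%, width 0.165. All 17 rows of the N = 100 column of Table 19 reproduce to 0.1 point. (The text attributes 0.165 to an asymptotic formula. The Wald width is 2 × 1.96 × √(0.2 × 0.8/100) = 0.157, so the quoted figure is the exact one.)

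**Per arm against pooled, exact limits, in %:**

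| Observed rate | N = 100 | Width | N = 200 | Width | Ratio of widths |
|---|---|---|---|---|---|
| 0 | 0 to 3.6 | 3.62 | 0 to 1.8 | 1.83 | 1.98 |
| 5 | 1.6 to 11.3 | 9.64 | 2.4 to 9.0 | 6.58 | 1.465 |
| 10 | 4.9 to 17.6 | 12.72 | 6.2 to 15.0 | 8.81 | 1.445 |
| 20 | 12.7 to 29.2 | 16.52 | 14.7 to 26.2 | 11.53 | 1.432 |
| 50 | 39.8 to 60.2 | 20.34 | 42.9 to 57.1 | 14.27 | 1.425 |
| 80 | 70.8 to 87.3 | 16.52 | 73.8 to 85.3 | 11.53 | 1.432 |

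With 90 against 180 the ratios barely move (1.468 at 5%, 1.433 at 20%).

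**Mean log antibody level.** Half-width = t × SD/√n. With SD 0.83 this is 0.165 at n = 100 and 0.116 at n = 200, ratio 1.423. If both use the common residual variance of the ANCOVA, the ratio is √(200/100) = 1.414. Neither ratio depends on the value of the SD.

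**Would pooling help the third-dose comparison?** Assume equal SDs and a within-subject correlation r between the post-dose-2 and post-dose-3 levels, and work in units of variance/100.

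- Dose-3 mean minus the same arm's dose-2 mean: 1 + 1 − 2r = 2 − 2r.
- Dose-3 mean minus the pooled dose-2 mean: 1 + 0.5 − 2 × 0.5r = 1.5 − r.

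The pooled reference is better only if r < 0.5. The documents do not give r. At r = 0.3 the variances are 1.4 and 1.2; at r = 0.5 both are 1.0; at r = 0.8 they are 0.4 and 0.7, so the pooled version has an interval √(0.7/0.4) = 1.32 times as wide.

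**Chance differences.** Four antigens × two time points (Days 91 and 181) × two measures (GMC and GMR ratios) gives 16 between-group contrasts before the regimens differ. If there is no true difference, 16 × 0.05 = 0.8 of them are expected to have a 95% CI excluding 1.

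**The case against.** The strongest reply is that the plan delivers what it promises. The endpoints are defined within each vaccination schedule, and the stated intention (Protocol 10.10, SAP 7) is to estimate safety and immune response after a third injection. Two-dose schedules were studied in earlier trials. That stands: by-arm reporting is not an error, and a pooled column would be an addition.

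Four further points limit the concern:

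- **Third dose.** A reader might infer that by-arm reporting makes the reference for the third dose needlessly noisy. The documents do not support this. The planned antibody contrasts are within subject and within arm (the one-sample calculation in Protocol 10.4; GMRs against Day 181 and Day 361 in SAP 6.4.1.1.1). A pooled reference would widen the dose-3 against dose-2 contrast whenever r exceeds 0.5. For Schedule 2 the pre-third-dose level is Day 361, after the arms have diverged.
- **Chance.** A reader might infer that any arm difference before the Day 181 injection must be chance. That follows from randomisation for all randomised subjects, but the first-line antibody analysis uses the PPS. Its medication and medical-condition criteria run to Day 391, and its visit windows extend beyond Day 181 (SAP 5.1.3; Protocol Table 6). Some exclusions are right-censored by visit (SAP 5.2.3.2), but those for medical conditions, vaccination schedule and sample timing are not listed there. PPS membership at Days 91 and 181 can therefore depend on later events.
- **Lost data.** Nothing is discarded. For AE and seropositivity rates, a reader can add the two arms' counts and compute the pooled interval.
- **Absence.** The table list and mock tables (SAP 10 and Annex 3) are not among the documents, so a total column there cannot be ruled out. The SAP text describes none.

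It is also fair to say that a pooled column does not hide chance differences, since the by-arm columns remain. SAP 6.4.1.1.2 already calls the between-group analyses exploratory; labelling is the remedy for that part.

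**Conclusion.** The point holds as a modest, inexpensive gain in precision. For stand-alone estimates in the common period, per-arm intervals are 42% to 47% wider than pooled ones for AE rates between 5% and 80%, and 41% to 42% wider for mean log antibody levels. With zero events the per-arm upper limit is about double (3.6% against 1.8%).

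This assumes equal arms near the planned size and, for antibodies, an analysis set that does not depend on what happens after Day 181. The case is firmest for AEs, which are analysed on the safety sets and are components of the primary endpoint. It is optional for antibodies. The sample size, the third-dose estimates and the within-subject third-dose GMRs are untouched, and those GMRs should stay within arm.

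**What to change.** 1. In SAP 6.5.1 and 6.5.2.3, add a both-schedules column with exact 95% CI for solicited and unsolicited AEs after Dose 1 and after Dose 2, on the safety sets already defined. Do not extend it to the injections at Days 181 and 361, where the arms receive different products.
2. Optionally, in SAP 6.4.1.1.1, add descriptive pooled GMC and seropositivity at Days 1, 91 and 181, and pooled GMR against Day 1 at Days 91 and 181. State the analysis set: either the FAS, or the PPS with a note that its exclusions extend past Day 181. SAP 6.4.1 runs the FAS only if more than 10% are excluded from the PPS, so choosing the FAS means producing these few summaries regardless.
3. Keep the by-arm columns, and label differences between arms before the Day 181 injection as a randomisation check.

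The cost is one extra column in existing tables. No new data, endpoint or method is needed.

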**Table 11 Study vaccines**

| Treatment name | Vaccine/
product name | Formulation   | Presentation                           | Volume to
be
administered | Number of
doses |
|----------------|--------------------------|---|--|---------------------------------|--------------------|
| 10-10-3/AS01E  | NTHi-Mcat 10-10-3        | PD=10µg; PE-PilA=10µg;
UspA2=3.3µg   | Freeze-dried antigens in monodose vial | 0.5 ml                          | 3                  |
|                | AS01E                    | MPL=25µg; QS21=25µg;
Liposomes   | Liquid in monodose vial                |                                 |                    |
| Placebo        | Formulation buffer S9b   | Na 2 HPO 4 =0.4mg;
KH 2 PO 4 =56µg;
NaCl=1,16mg; KCl=30µg;
MgCl 2 =15µg | Liquid in monodose vial                | 0.5 ml                          | 1                  |

**MPL** = 3-O-desacyl-4'-monophosphoryl lipid A; **QS-21** = Quillaja saponaria Molina, fraction 21 (Licensed by GSK from Antigenics Inc, a wholly owned subsidiary of Agenus Inc., a Delaware, USA corporation).

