**10.8. Analysis of safety**

The analysis for safety will be performed on the ES.

The number and percentage of subjects with at least one **local solicited AE**, with at least one **general solicited AE** and with any solicited AE during the 7-day follow-up period after each vaccination, will be tabulated with exact 95% confidence interval (CI), after each vaccination and overall by study group. The percentage of doses followed by at least one local solicited AE, by at least one general solicited AE and by any solicited AE will be tabulated overall by group with exact 95% CIs. The same computations will be done for Grade 3 solicited AEs.

The number and percentage of subjects reporting each individual solicited local and general AE during the 7-day follow-up period will be tabulated with exact 95% CI after each vaccination and overall by vaccine schedule. The percentage of doses followed by each individual solicited local and general AE will be tabulated overall by group with exact 95% CIs.

The same tabulation will be performed for Grade 3 AEs.

For fever, additional analyses will be performed by 0.5°C increments.

**CONFIDENTIAL**207759 (NTHI MCAT-008)  
Protocol Amendment 3 Final

All the unsolicited adverse events occurring within 30 days after each vaccination, judged either as probably related, possibly related, or not related to vaccination by the investigator, will be recorded.

The verbatim reports of **unsolicited** symptoms will be reviewed by a physician and the signs and symptoms will be coded according to the MedDRA Dictionary for Adverse Reaction Terminology. Every verbatim term will be matched with the appropriate preferred term (PT). The percentage of subjects with at least one unsolicited AE during the 30-day follow-up period after any study vaccination will be tabulated with its exact 95% CI for each group and by MedDRA PT. Similar tabulation will be done for the percentage of doses, for Grade 3 unsolicited symptoms.

The number of subjects who experienced any **pIMD** or any **SAE** from first vaccination up to 12 months post-Dose 4 will be reported.

The number of subjects who experienced any **SAE, death, pIMD or AE leading to study withdrawal**, from first vaccination up to study conclusion, and any **SAE related to study participation of concurrent GSK medication/ vaccination**, during the entire study period, will be reported.

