## 2. STUDY DESIGN

**Figure 1 Study design overview**

**Experimental design:** Phase II, observer-blind, randomised, multi-centric study with two parallel groups.

**Duration of the study:** for each subject enrolled, the study will last approximately 2 years from Visit 1 (enrolment visit):

- Epoch 001 : Primary (Vaccination phase) starting at Visit 1 (Day 1) and ending at Visit 9 (Day 541).
- Epoch 002 : Long-term follow-up starting after Visit 9 (Day 541) and ending at Visit 10 (Day 721).

Primary Completion Date (PCD): Visit 9 (Day 541).

Refer to the Glossary of terms of the protocol for the definition of PCD.

**End of Study (EoS):** Last testing results released of samples collected at Visit 10 (Day 721).

Refer to the Glossary of terms of the protocol for the definition of EoS.

**CONFIDENTIAL**207759 (NTHI-MCAT-008)  
Statistical Analysis Plan Amendment 1 Final

Study groups:

- **Schedule 1** : Approximately 100 subjects receiving three doses of the AS01E-adjuvanted GSK Biologicals' NTHi-Mcat investigational vaccine containing 10 µg of PD, 10 µg of PE-PilA, and 3.3 µg of UspA2 at Visit 1 (Day 1), Visit 3 (Day 61) and Visit 5 (Day 181) and one dose of placebo at Visit 7 (Day 361).
- **Schedule 2** : Approximately 100 subjects receiving three doses of the AS01E-adjuvanted GSK Biologicals' NTHi-Mcat investigational vaccine containing 10 µg of PD, 10 µg of PE-PilA, and 3.3 µg of UspA2 at Visit 1 (Day 1), Visit 3 (Day 61) and Visit 7 (Day 361) and one dose of placebo at Visit 5 (Day 181).

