**10. LIST OF FINAL REPORT TABLES, LISTINGS AND FIGURES**

The TFL TOC provides the list of tables/listings and figures needed for the study report. It also identifies the tables eligible for each analysis and their role (synopsis, in-text, post-text, SHS, CTRS,...). Note that all TFL aimed to be included as post-text are noted as post-text even if these are tabulation of individual data such as listing of SAE. The post-text material contains all source material for the study report and accordingly a post-text table may be redundant with an in-text table.

The following group names will be used in the TFLs:

Group order in tables	Group label in tables	T-domains	Group definition for footnote
1	Schedule 0-2-6	Schedule 1	Third dose at six months.
2	Schedule 0-2-12	Schedule 2	Third dose at one year.

The group names in the Protocol, Schedule 1 and Schedule 2, will be renamed as Schedule 0-2-6 and Schedule 0-2-12, respectively, in all the statistical analyses and in the study report.

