**11.2.2. Dose number**

- The study dose number is defined in reference to the number of study visits at which vaccination occurred. More specifically dose 1 refers to all vaccines administered at the first vaccination visit while dose 2 corresponds to all vaccinations administered at the second vaccination visit even if this is the first time a product is administered to the subject.
- Relative dose: the relative dose for an event (AE, medication, vaccination) is the most recent study dose given before an event. In case the event takes place on the day a study dose is given, the related dose will be that of the study dose, even if the event actually took place before vaccination. For instance, if an adverse event begins on the day of the study vaccination but prior to administration of the vaccine, it will be assigned to this dose. In case a study dose is not administered and an event occurs after the subsequent study dose (e.g. 3rd study dose), the relative dose of the event will be study dose associated to the subsequent study dose (e.g. dose 3).
- The number of doses for a product is the number of time the product was administered to a subject.
- The incidence per dose is the number of vaccination visits at which an event was reported among all vaccination visits.

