- the duration of solicited adverse events will be calculated as the sum of the consecutive days with the symptom reported at Grade 1 or higher. The duration of solicited events at a specific grade (e.g., Grade 3) will be calculated as the sum of the consecutive days with the symptom reported at that grade. The same rule applies for solicited adverse events ongoing at the end of the solicited follow-up period considering the maximum intensity reported;
- when the occurrences of solicited adverse events are summarised, each event recorded as having occurred during a specific period will be counted as the number of occurrences the event is consecutively reported (at Grade 1 or higher);
- when the occurrences of solicited adverse events at a specific grade are summarised, each event recorded as having occurred at that grade during a specific period will be counted as the number of occurrences the event is consecutively reported at that grade.

For analysis of unsolicited adverse events, such as serious adverse events or adverse events by primary MedDRA term, and for the analysis of concomitant medications, all vaccinated subjects will be considered. Subjects who did not report the event or the concomitant medication will be considered as subjects without the event or the concomitant medication respectively. Note that for all tables described in this section, the way the percentage of subjects will be derived will depend on the event analysed (see table below for details). As a result, the N value will differ from one table to another.

**CONFIDENTIAL**207759 (NTHI MCAT-008)  
Statistical Analysis Plan Amendment 1 Final

Event	N used for deriving % per subject for Vaccination phase	N used for deriving % per dose for Vaccination phase
Concomitant vaccination	All subjects with study vaccine administered	
Solicited local/general symptom	All subjects, with study vaccine administered, with at least one solicited symptom, either local or general, documented as either present or absent (i.e., symptom screen completed)	All study visits with study vaccine administered and with at least one solicited symptom, either local or general, documented as either present or absent (i.e., symptom screen completed)
Unsolicited symptom with onset within 30 days	All subjects, with study vaccine administered, that have safety data	
Unsolicited symptom (e.g., SAEs, AEs leading to withdrawal,..)	All subjects with study vaccine administered	

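### The per-dose solicited-AE percentages pool vaccine and placebo injections, and their exact CIs treat up to four records per subject as independent

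*SAP*

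**What the plan says.** For each individual solicited symptom, SAP 6.5.1 states: "percentage of doses followed by each individual solicited local and general AE will be tabulated overall by group and by severity with exact 95% CIs". Protocol 10.8 has the same table without the severity breakdown: "The percentage of doses followed by each individual solicited local and general AE will be tabulated overall by group with exact 95% CIs".

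The counting rule is in SAP 11.2.2: "The incidence per dose is the number of vaccination visits at which an event was reported among all vaccination visits". The denominator table in SAP 11.2.5 restricts this to visits with a documented screen: "All study visits with study vaccine administered and with at least one solicited symptom". Placebo counts as a study vaccine here. The protocol glossary includes placebo in its entry for study vaccine/product, and the table in Protocol 6.1 titled "Table 11 Study vaccines" has a placebo row.

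Under SAP section 2, every subject attends four vaccination visits, three with NTHi-Mcat and one with placebo. The placebo visit is Day 361 in Schedule 1 and Day 181 in Schedule 2.

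SAP 11.2.2 also defines a count by product, "The number of doses for a product is the number of time the product was administered to a subject", but SAP 6.5.1 does not apply it to the per-dose percentages. SAP section 10 keeps the table list elsewhere ("The TFL TOC provides the list of tables/listings and figures needed for the study report"). That list and the shells were not available for this review, so a product split may exist there.

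**The concern.** There are two separate problems with the same table.

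**What is estimated.** The primary objective concerns the reactogenicity of the NTHi-Mcat vaccine under two schedules. A figure in which about one record in four is a placebo injection answers a different question from the rate per vaccine dose. If the vaccine is more reactogenic than placebo, a reader who takes the pooled figure as the vaccine rate reads it too low.

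**How precisely.** A one-proportion exact interval assumes independent records with one common rate. Here the same subject supplies up to four records, and the product changes within the subject. If some subjects tend to react repeatedly, the interval can be too narrow. If the vaccine and placebo rates differ widely, it can be too wide.

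The SAP describes its safety analyses as estimation, so an interval that does not hold its stated confidence is a defect even where nothing is tested.

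**Working it through.** **Inputs from the documents.** 100 subjects per group (Protocol 10.4); four vaccination visits, three vaccine and one placebo (SAP section 2); two-sided 95% intervals (SAP 11.2.4). Clopper-Pearson is the only one-proportion exact method the SAP references (6.4.2.1 and 11.1), so exact is read as that.

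**The plan's own figure.** Protocol 10.4 gives a width of 0.165 at 20% with N = 100. Clopper-Pearson on 20/100 gives 12.7% to 29.2%, width 0.165, so it reproduces. It rests on one record per subject. The documents state no precision for the per-dose percentages.

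**Assumed inputs.** The documents give no vaccine rate p, placebo rate q or within-subject correlation. Each is assumed over a range below.

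**Step 1: the pooled rate.** With all doses recorded, pooled rate = 0.75p + 0.25q, so the shortfall against p is (p − q)/4. At 20%/5% the pooled rate is 15 + 1.25 = 16.25%, a shortfall of 3.75 points. At 80%/10% it is 60 + 2.5 = 62.5%, a shortfall of 17.5 points.

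**Step 2: the direction of the interval error.** Compare the true variance of a subject's four records with the binomial value at the pooled rate.

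- Independent records, 80%/10%: (3 × 0.8 × 0.2 + 0.1 × 0.9) / (4 × 0.625 × 0.375) = 0.57/0.9375 = 0.61. The interval is too wide.
- Independent records, 20%/5%: (3 × 0.2 × 0.8 + 0.05 × 0.95) / (4 × 0.1625 × 0.8375) = 0.5275/0.5444 = 0.97. There is almost no error.
- At the highest assumed correlation these ratios rise to 1.11 and 1.89.

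If all four doses share one rate, the design effect is 1 + 3 × ICC and coverage is roughly 2Φ(1.96/√DE) − 1. ICC 0.1 gives DE 1.3 and 91.4%. ICC 0.3 gives DE 1.9 and 84.5%.

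**Step 3: coverage by simulation.** 100 subjects, four records each, a shared Gaussian latent subject effect with correlation 0, 0.2, 0.4 and 0.6, 20,000 runs per cell. ICC is the binary ICC among vaccine doses. Pooled coverage is for the pooled rate itself; vaccine-only coverage is for p.

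| p / q | Shortfall (points) | ICC range | Pooled exact CI, coverage % at the four correlations | Vaccine doses only, exact CI, coverage % |
|---|---|---|---|---|
| 20% / 5% | 3.75 | 0 to 0.37 | 95.9, 93.5, 90.3, 86.1 | 95.6, 93.5, 90.9, 87.4 |
| 80% / 10% | 17.5 | 0 to 0.37 | 99.0, 97.9, 96.4, 94.4 | 95.6, 93.1, 90.6, 87.1 |
| 5% / 1% | 1.0 | 0 to 0.27 | 96.0, 94.8, 92.2, 88.8 | 96.7 to 91.4 |
| 2% / 0.5% | 0.375 | 0 to 0.22 | 97.6, 96.8, 95.4, 93.1 | 96.6 to 92.4 |
| 1% / 0.2% | 0.2 | 0 to 0.18 | 98.3, 98.0, 97.3, 95.9 | 98.8 to 97.3 |

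The last column shows that splitting by product does not by itself repair the interval at common rates.

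**Step 4: candidate repairs.**

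- *Clopper-Pearson with events and doses both divided by the estimated design effect (floored at 1).* Coverage is 95.2% to 98.8% over the 20 vaccine-only cells and 95.5% to 99.0% over the 20 pooled cells. With some doses unrecorded (100%, 97% and 90% recorded) and equal or unequal dose rates, 28 vaccine-only cells gave 94.5% to 98.9%, against 87.5% to 98.8% unadjusted.
- *Subject-clustered robust interval.* About 94% to 95% at 20%/5% and 80%/10%, but 89% to 85% (pooled) at 2%/0.5% and 83% to 77% (pooled) at 1%/0.2%. With no events in 300 vaccine doses it collapses to 0 to 0, where the exact upper limit is 1 − 0.025^(1/300) = 1.2%.
- *Exact interval for placebo doses alone (one record per subject).* 95.4% or more in every cell.

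**The case against.** The strongest reply is that little depends on this table. The primary endpoint is occurrence after each vaccination within each schedule. SAP 6.5.1 tabulates that per subject with exact intervals, and the visit number together with the group identifies the product. The per-dose table carries no test or rule. All of this stands, and it limits the consequence.

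Second, the pooled figure is not wrong in itself. It is a true rate per injection in a schedule that includes a placebo visit. This also stands: harm requires a reader to take it as the vaccine rate, which the SAP does not claim it to be.

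Third, the coverage loss depends wholly on assumed rates and correlation. At zero correlation there is none, and at 80%/10% pooled coverage stays above 95% at three of the four correlations. The movement in the limits is modest: at 20%/5% and the highest correlation the mean pooled width goes from 7.4 to 10.3 points, about 1.45 points on each side. That is a fair limit on the size. It does not justify an independence assumption that repeated records from the same subjects give no reason to expect.

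Fourth, Protocol 10.8 itself prescribes the exact interval, so replacing it departs from the protocol. This is correct and adds a documentation step, but it does not make the interval valid.

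**Conclusion.** The concern holds. As written, the per-dose percentages mix products 3:1, and their exact intervals ignore repeated records per subject.

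The shortfall of (p − q)/4 against the vaccine rate is exact when all doses are recorded. The loss of coverage is conditional on positive within-subject correlation and is mainly a matter of common, any-grade symptoms. Under the assumed ranges the pooled interval falls to about 86% at worst (20%/5%, ICC 0.37). For events at about 2% or less, such as many Grade 3 symptoms, it stays close to or above 95% unless the correlation is high. With very different product rates and little correlation it is too wide.

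This should be corrected, but the consequence is limited: the table is supplementary and the primary per-subject results are unaffected. Confidence is medium, because the rates and correlation are assumptions and the table shells were not available.

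**What to change.** Amend SAP 6.5.1, 11.2.2 and 11.2.5 as follows.

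1. Report per-dose percentages separately for NTHi-Mcat doses and placebo doses, using the count by product that SAP 11.2.2 already defines.
2. Keep the exact interval for placebo doses.
3. For NTHi-Mcat doses, and for any pooled total that is kept, either give no interval or use Clopper-Pearson with events and doses both divided by the estimated within-subject design effect. That is the subject-clustered variance of the percentage divided by its binomial variance, set to at least 1, and to 1 when there are no events.
4. Do not use an unmodified GEE, robust or bootstrap interval for rare or zero-count Grade 3 events.
5. State the product received in tables labelled by visit-numbered dose.
6. Leave the exact intervals in the per-subject tables as they are.

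The cost is SAP wording and minor table programming, with no new data and no change to the primary tables. Because Protocol 10.8 specifies exact intervals here, record the change in SAP section 9 (now marked not applicable) and justify it in the study report, as Protocol 10.11 requires. The adjusted vaccine-dose intervals are wider: at p = 20% the mean width goes from 9.3 points to 9.6 (ICC 0) and up to 12.4 (ICC 0.37), and at p = 1% from 2.6 to at most 3.0 points.
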